## PROTOCOL SYNOPSIS

Title:	A RANDOMIZED, DOUBLE-BLIND, PLACEBO-CONTROLLED TRIAL TO EVALUATE THE EFFICACY AND SAFETY OF LEBRIKIZUMAB IN PATIENTS WITH MODERATE-TO-SEVERE ATOPIC DERMATITIS
Protocol Number:	DRM06-AD04
Phase:	3
Number of Sites:	Approximately 100 sites in the United States (US), European Union (EU) and Asia/Pacific region.

Study Population: Adolescent patients (<math>\geq 12</math> to <math>< 18</math> years weighing <math>\geq 40</math> kg) and adults with moderate-to-severe atopic dermatitis (AD) who are candidates for systemic therapy.
 
Sample Size: Approximately 400 patients with moderate-to-severe AD, including approximately 50 adolescent patients.
	

Study Objectives: To evaluate the safety and efficacy of lebrikizumab compared with placebo in patients with moderate-to-severe AD.
	

Duration of Patient Participation: Screening: Maximum duration of 30 days Induction Period: 16 weeks Maintenance Period: 36 weeks Safety Follow Up: 12 weeks Maximum total participation: 66 weeks For patients terminating early or not rolling into the long-term extension study (LTE), a safety follow-up visit will occur 12 weeks after last dose of study medication. Completion of patient participation: A patient is considered to have completed the study if he/she has completed the last scheduled visit:
 
 
• For subjects continuing into LTE, upon completion of week 52 visit and rolling into LTE study
 
	

- For subjects not continuing into LTE, when subject had either week 52 or Early Termination Visit (ETV), and safety follow up visit (12 weeks after last IP administration)

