
Primary percentage of patients with an IGA score of 0 or 1 and a reduction ≥ 2 points from Baseline to Week 16.
	
Co-primary Percentage of patients with an IGA score of 0 or 1 and a reduction ≥ 2 points from baseline to Week 16.
 
Percentage of patients achieving EASI-75 ($\geq 75\%$ reduction from Baseline in EASI score) at Week 16

Major Secondary
 
 Percentage of patients achieving EASI-75 ($\geq 75\%$ reduction from Baseline in EASI score) at Week 16 Percentage of patients achieving EASI-90 ($\geq 90\%$ reduction from Baseline in EASI score) at Week 16 Percentage of patients with a Pruritus Numerical Rating Scale (NRS) of ≥ 4-points at Baseline who achieve a ≥ 4-point reduction from Baseline to Week 16 Percentage of patients with a Pruritus NRS of ≥ 4-points at Baseline who achieve a ≥ 4-point reduction from Baseline to Week 4 Percentage of patients with a Pruritus NRS of ≥ 4-points at Baseline who achieve a ≥ 4-point reduction from Baseline to Week 2 Percentage of patients with an IGA score of 0 or 1 and a reduction ≥ 2 points at Week 4. Percentage of patients with an IGA score of 0 or 1 and a reduction ≥ 2 points at Week 16 in adults. Percentage of patients with a Sleep-loss score ≥ 2 points at Baseline who achieve a ≥ 2 points reduction from Baseline at Week 16 	
Major Secondary Endpoints Specific for Induction Period
 
 Percentage of patients achieving EASI-90 at Week 16 Percentage of patients achieving EASI-90 at Week 4 Percentage change in EASI score from Baseline to Week 16 Percentage change in Pruritus NRS score from Baseline to Week 16 Percentage of patients with a Pruritus NRS of ≥ 4-points at Baseline who achieve a ≥ 4-point reduction from Baseline to Week 16 Percentage of patients with a Pruritus NRS of ≥ 4-points at Baseline who achieve a ≥ 4-point reduction from Baseline to Week 4 Percentage of patients with a Pruritus NRS of ≥ 4-points at Baseline who achieve a ≥ 4-point reduction from Baseline to Week 2 Change from baseline in DLQI total score at Week 16 Percentage of patients with a DLQI total score of ≥ 4-points at Baseline who achieve a ≥ 4-point improvement from baseline to Week 16 Change from Baseline in Sleep-loss score at Week 16 Percentage of patients with a Sleep-loss score ≥ 2 points at Baseline who achieve a ≥ 2 points reduction from Baseline at Week 16

Objectives and Endpoints

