6.1.1. Analysis Populations

Analysis populations are defined in [Table KGAB.6.1](#) along with the analysis they will be used to conduct. [Table KGAB.6.2](#) describes the treatment groups and the comparisons for each study period and the analysis population.

[Figure KGAB.6.1](#) shows a pictorial description of all the analysis populations.

[figure not shown]

Figure KGAB.6.1. Study periods and analysis populations.

Table KGAB.6.1. Analysis Populations

Population	Description
All Entered Patients	All patients who signed informed consent. Patient flow will be summarized.
Intent-to-Treat (ITT) Population	All randomized patients, even if the patient does not take the assigned treatment, does not receive the correct treatment, or otherwise does not follow the protocol. Patients will be analyzed according to the treatment to which they were assigned. Unless otherwise specified, efficacy and health outcomes analyses for the Induction period will be conducted on this population.
Safety Population	All randomized patients who received at least 1 dose of study treatment during Induction Period. Safety analyses for Induction period will be conducted on this population.
Maintenance Primary Population (MPP)	All patients who were randomized to Lebrikizumab 250 mg Q2W at Baseline Visit and re-randomized to Lebrikizumab 250 mg Q2W, Lebrikizumab 250 mg Q4W or placebo at Week 16 and received at least 1 dose of study treatment during the maintenance period. Patients will be analyzed according to the treatment to which they were re-randomized. Only information prior to escape will be presented. Efficacy, health outcomes, and safety analyses for the maintenance period will be conducted on the Maintenance Primary population
Maintenance Secondary Population (MSP)	Including patients who were randomized to placebo at Baseline Visit and re-randomized to Lebrikizumab 250 mg Q2W, Lebrikizumab 250 mg Q4W or placebo at Week 16, and received at least one dose of study treatment during the maintenance period. Selective efficacy analyses for the maintenance period will be conducted on the Maintenance Secondary Population. Patients will be analyzed according to the treatment to which they were re-randomized. Only information prior to escape will be presented.

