6.4.1.1. Markov Chain Monte Carlo Multiple Imputation (MCMC-MI)

The primary method of handling missing efficacy data relative to the primary estimand will be as follows for both binary and continuous endpoints:

For patients who receive topical rescue medication (per Protocol Section 6.3), receive systemic rescue medication, or discontinue treatment due to lack of efficacy, set to the patient's baseline value subsequent to this time through Week 16. The MCMC-MI will be used to handle the remaining missing data. Imputation will be conducted within each treatment group independently so the pattern of missing observations in one treatment group cannot influence missing value imputation in another. The SAS PROC MI with MCMC option will be used to conduct the MCMC-MI. The imputation model will include the relevant baseline and post-baseline.

For each imputation process, 25 datasets with imputations will be calculated. The initial seed values are given in [Table KGAB.6.7](#). Each complete data set will be analyzed with the specified analysis. The results from these analyses will be combined into a single inference using SAS PROC MIANALYZE.

Cochran-Mantel-Haenszel (CMH) test statistic will be transformed using the Wilson-Hilferty transformation and then standardized (Ratitch 2013) prior to combining them using SAS PROC MIANALYZE. Details of combining estimates and test statistics for categorical endpoints with multiple imputation can be found in [Appendix 2](#).

For binary responses related to EASI and IGA, the binary response variables will be calculated based on the multiply imputed datasets that have been created. Because the MCMC algorithm is based on the multivariate normal model, imputed values for IGA will not generally be one of the discrete values used in IGA scoring (0, 1, 2, 3, or 4). Therefore, to derive the binary IGA response variable, standard rounding rules will be applied to the imputed values. For example, if a patient has an IGA score imputed as 1.4 (and assuming a Baseline IGA score of 3), the imputed value would be rounded down to 1, and the minimum change from Baseline of 2 would have been met. This patient would be considered a responder.

For derivation of an EASI-75 and EASI-90 response, no rounding will be performed. The imputed Week 16 EASI value will be compared directly to the observed Baseline EASI value to determine whether a reduction of at least 75% or 90% was achieved.

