	
DLQI daily activities domain
	
Sum of responses of questions #3 and #4: #3. How much has your skin interfered with you going shopping or looking after your home or garden? #4. How much has your skin influenced the clothes you wear?
	
If 1 question in a domain is missing, that domain is missing.

		DLQI leisure domain	Sum of responses of questions #5 and #6: #5. How much has your skin affected any social or leisure activities? #6. How much has your skin make it difficult for you to do any sport?	If 1 question in a domain is missing, that domain is missing.
		DLQI work and school domain	Sum of responses of questions question #7A and #7B: #7A. Has your skin prevented you from working or studying? #7B. If No: how much has your skin been a problem at work or studying?	If the answer to question #7A is missing, this domain is missing. If #7A is No, and #7B is missing, this domain is missing.
		DLQI personal relationships domain	Sum of responses of questions #8 and #9: #8. How much has your skin created problems with your partner or any of your close friends or relatives? #9. How much has your skin caused any sexual difficulties?	If 1 question in a domain is missing, that domain is missing.
		DLQI treatment domain	Response of question #10: #10. How much of a problem has the treatment for your skin been, for example by making your home messy, or by taking up time?	If 1 question in a domain is missing, that domain is missing.
Children's Dermatology Life Quality Index (CDLQI)	The CDLQI is designed to measure the impact of any skin disease on the lives of children. Patients ≤16 years will complete the CDLQI and should continue to complete the CDLQI for the duration of the study. The scoring of each question is: 
 • Very much = 3 • Quite a lot = 2 • Only a little = 1 	CDLQI total score	A CDLQI total score is calculated by summing all 10 question responses and has a range of 0-30 (less to more impairment) (Waters et al. 2010).	Score of 1 unanswered question = 0; If 2 or more questions are missing, the total score is missing.
		CDLQI (0,1)	A CDLQI (0,1) response is defined as a postbaseline CDLQI total score of 0 or 1.	Missing if CDLQI total score is missing
		4-point improvement	Change from baseline ≤-4	Missing if baseline is missing or observed value is missing.

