	Proportion of patients achieving at least 2-point improvement in Sleep-loss in patients who had baseline Sleep-loss ≥ 2	NA	Descriptive statistics	Maintenance W16 Escape Population with Baseline Sleep-loss score at least 2	No comparisons. all scheduled visits in Maintenance Period	Secondary analysis
(Children) Dermatology Life Quality Index (DLQI/ CDLQI)	Change from baseline in DLQI total score	Primary Estimand (Hybrid)	ANCOVA with MCMC-MI	ITT	Leb 250 mg Q2W vs PBO; Week 16 and all scheduled visits in Induction Period	Key secondary analysis: W16 for DLQI chg; Secondary analysis: other timepoints
	Change from baseline in DLQI total score	Supportive Estimand (Hypothetical)	MMRM with observed data	ITT	Leb 250 mg Q2W vs PBO; Week 16 and all scheduled visits in Induction Period	Supplementary analysis for DLQI; Secondary analysis for CDLQI
	Change from baseline in CDLQI total score					
	Change from baseline in DLQI total score	Maintenance Supportive Estimand (Hypothetical)	ANCOVA with LOCF	Maintenance Primary Population	Leb 250 mg Q2W vs PBO; Leb 250 mg Q4W vs PBO; all scheduled visits in Maintenance Period	Secondary analysis
	Change from baseline in CDLQI total score					

Measure	Variable	Estimand (Section 6.2)	Analysis Method (Section 6.1)	Population (Section 6.1.1)	Comparison/Time Point	Analysis Type
	Change from baseline in DLQI total score	NA	Descriptive stats	Maintenance W16 Escape Population	No comparisons. all scheduled visits in Maintenance Period	Secondary analysis
	Change from baseline in CDLQI total score					
	Proportion of patients achieving at least 4-point improvement in DLQI	Primary Estimand (Hybrid)	CMH analysis with MCMC-MI	ITT, ITT with Baseline DLQI score at least 4	Leb 250 mg Q2W vs PBO; Week 16 and all scheduled visits in Induction Period	Key secondary analysis: W16 for ITT with Baseline DLQI score at least 4, Secondary analysis: other timepoints and population
		Supportive Estimand (Composite)	CMH analysis with NRI	ITT with Baseline DLQI score at least 4	Leb 250 mg Q2W vs PBO; Week 16 and all scheduled visits in Induction Period	Supplementary analysis
	Proportion of patients achieving ≥ 4 point improvement in DLQI in patients who had baseline DLQI score ≥ 4	Maintenance Supportive Estimand (Composite)	CMH with NRI	Maintenance Primary Population with baseline DLQI score at least 4	Leb 250 mg Q2W vs PBO; Leb 250 mg Q4W vs PBO; all scheduled visits in Maintenance Period	Secondary analysis

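### Would patients aged 16 or under, who never complete the DLQI, be imputed into the EMA's DLQI endpoint?

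*SAP*

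**What the plan says.** **The endpoint.** SAP Table KGAB.4.1 lists "Change from baseline in DLQI total score at Week 16" among the EMA major secondary endpoints for induction, and Section 6.6.2 places it in the testing scheme. Table KGAB.6.12 gives the method as "ANCOVA with MCMC-MI", the population as ITT without qualifier, and the type as "Key secondary analysis: W16 for DLQI chg". Table KGAB.6.1 defines ITT as all randomized patients and adds: "Unless otherwise specified, efficacy and health outcomes analyses for the Induction period will be conducted on this population".

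The EMA scheme holds a second DLQI endpoint, the 4-point response, which Table KGAB.6.12 labels "Key secondary analysis: W16 for ITT with Baseline DLQI score at least 4". A version of that response in unrestricted ITT is also listed, but only as an ordinary secondary analysis outside the testing scheme.

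**The questionnaire.** SAP Table KGAB.6.11 says: "Patients ≤16 years will complete the CDLQI and should continue to complete the CDLQI for the duration of the study". Protocol Section 8.3.2 has the same rule. The Protocol Synopsis plans for "Approximately 400 patients with moderate-to-severe AD, including approximately 50 adolescent patients".

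**Missing data.** SAP Section 6.4.1.1 first sets patients with rescue, or with discontinuation for lack of efficacy, to their baseline value. Then: "The MCMC-MI will be used to handle the remaining missing data". Imputation is done within each arm, 25 times, from the relevant baseline and post-baseline values. The section names no age term and does not mention CDLQI completers.

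**The concern.** Put together, these entries seem to require imputation of a questionnaire in patients who were never given it. Someone aged 16 or under has no DLQI at baseline or later. If the ITT label and the imputation rule are both applied literally, the procedure must draw a baseline and a Week 16 value for that patient from the DLQI completers in the same arm. If baseline is drawn, membership of the subgroup with baseline DLQI of at least 4 could also vary between imputed datasets.

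The SAP does restrict the population for other instruments not given to everyone. The ACQ-5 is limited to patients with asthma, and the SQAAQ to those who complete it. The absence of a restriction for the DLQI therefore looks like an oversight.

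At stake would be a multiplicity-controlled quality-of-life result presented as covering all randomized patients, although some adolescents contributed no DLQI information, and a sample size that two programmers might derive differently.

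**Working it through.** **1. The plan's own figures.** The documents give no sample size or power for the DLQI and no count of patients aged 16 or under. The only sizing claim is more than 95% power for each co-primary endpoint with 96 versus 48 patients. It reproduces with the continuity correction (95.1% for IGA 0/1 at 34.7% versus 7.7%; 99.6% for EASI-75 at 48.0% versus 11.5%), but it does not bear on this point.

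**2. Which reading fits the rest of the SAP?**

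| SAP text | What it implies |
|---|---|
| Table KGAB.6.12, induction MMRM row shared by DLQI and CDLQI, population ITT | Taken literally, CDLQI would cover the 400 - 50 = 350 adults who never complete it. Here ITT can only be the parent set, with the instrument deciding who contributes. |
| Revision history, version 2 (entries for Sections 6.8.1 and 6.11) | The two instruments were split because they serve different groups of patients. |
| Table KGAB.6.6 | CDLQI has its own MMRM without imputation. |
| Section 6.4.1.1, EASI and Pruritus NRS responses | Imputed values are compared with an observed baseline. |
| Section 6.4.1.1, rescue or lack of efficacy | Value is set to baseline. This cannot be done for a CDLQI completer, who has no DLQI baseline. |
| Table KGAB.6.11, DLQI change | Missing when baseline is missing. |

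The literal reading cannot be carried out for every patient. Restricting the analysis to patients assigned the DLQI can.

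**3. How many patients?** Inputs: 400 patients, 50 adolescents (Protocol Synopsis). Assumption: a fraction f of the adolescents is aged 16 or under. Number without DLQI m = 50 × f; share = m/400; standard error relative to 400 observed patients = √(400/(400 - m)).

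| f | m | Share of ITT | Remaining | SE factor |
|---|---|---|---|---|
| 1/2 | 25.0 | 6.25% | 375.0 | 1.033 |
| 4/6 | 33.3 | 8.3% | 366.7 | 1.044 |
| 5/6 (ages 12 to 17 equally common) | 41.7 | 10.4% | 358.3 | 1.057 |
| 1 (ceiling) | 50.0 | 12.5% | 350.0 | 1.069 |

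The SE factor is not a loss caused by leaving these patients out. Their DLQI values do not exist under either reading.

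**4. Does imputing them change the result?** Let V be the variance of the estimate in DLQI completers. With 358.3 of 400 observed, the within-imputation variance is about 358.3/400 = 0.896 V and the between-imputation variance about 0.104 V. With 25 imputations the total is 0.896 V + (1 + 1/25) × 0.104 V = 1.004 V, so the standard error grows by √1.004 = 1.002.

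A simulation agrees. Its settings, all assumed apart from the 2:1 ratio, the total of 400 and the 25 imputations, were:
- 267 versus 133 patients;
- mean DLQI 15 at baseline and 10 at Week 16 on placebo, variance 49 at each time, covariance 20, treatment difference -2;
- 42/400 chance that a patient has no DLQI at all;
- within-arm draws, ANCOVA on treatment and baseline, 600 repetitions.

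| Analysis | Mean difference | Mean SE |
|---|---|---|
| DLQI completers only | -1.98 | 0.716 |
| All 400, the rest imputed within arm | -1.98 | 0.719 |

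A second run with a larger assumed effect gave -5.08 (SE 0.575) both ways. In it, imputation moved the difference in responder proportions by about 0.5 percentage points, in the slightly conservative direction.

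**The case for a change.** The strongest case for an amendment is that the text really is silent. The rule that change is missing without a baseline does not exclude anyone by itself: similar wording is attached to IGA response and EASI-75, which are imputed in full ITT. If programmers simply drop CDLQI completers, then ITT is a loose label. If they do not, a DLQI effect is attributed to adolescents who never answered the questionnaire. Either way, a sentence would settle it for an endpoint under Type I error control.

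Part of this stands: the label is imprecise and the SAP never says who is in the DLQI set. The rest carries less weight.

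- For IGA and EASI the entry criteria require a baseline score, so imputation there concerns later visits. A patient with no DLQI at any time is a different case, and the SAP does not say that baseline DLQI is to be imputed.
- The asthma contrast is only suggestive. The name ACQ-5 does not show that it is limited to patients with asthma, whereas the DLQI/CDLQI split is fixed by the age rule.
- The controlled 4-point response already requires a baseline DLQI of at least 4, so CDLQI completers are outside it unless baseline is imputed.
- The SAP states no DLQI sample size that could be wrong, and Protocol Section 9.1 includes the number of subjects among the descriptive statistics for continuous measures, so the number contributing will be visible.

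**Conclusion.** No change is needed. This is a gap that analysts fill sensibly: patients assigned the DLQI are analysed for the DLQI, and CDLQI completers are analysed for the CDLQI. The neighbouring table entries and the baseline-dependent imputation rules point that way.

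If someone did follow the letter, the conclusion would still stand. Patients drawn entirely from the same arm's completers add no information, and multiple imputation reflects that in its variance. The standard error changes from 0.716 to 0.719 and the estimate does not move. At most about 50 of 400 patients are concerned, and about 42 if ages are evenly spread.

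This rests on an assumed adolescent age distribution, on assumed DLQI means and covariance in the simulation, and on within-arm imputation as the SAP specifies. The figure showing the EMA testing graph is not available in the text reviewed, so the alpha reaching this endpoint could not be checked. That does not affect the argument, because the two readings give practically the same test.

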6.11.1. Primary Outcome and Methodology

The primary analysis of the study is to test the null hypotheses that lebrikizumab 250 mg Q2W is the same as placebo when evaluating the proportion of patients achieving IGA of 0 or 1 at Week 16 in the ITT population. For EMA, an additional null hypothesis is that lebrikizumab 250 mg Q2W is the same as placebo when evaluating the proportion of patients achieving EASI-75 at Week 16 in the ITT population.

The primary estimand for the primary analysis is described in Section 6.2.1.1. The missing data including those as a result of intercurrent events will be imputed using MCMC-MI based on missing at random assumption (Section 6.4.1.1).

A CMH test as described in Section 6.1.2 will be used for the comparisons. The odds ratio, the corresponding 95% CIs and p-value, as well as the treatment differences and the corresponding 95% CIs, will be reported.

Multiplicity controlled analyses will be performed on the primary and major secondary objectives to control the overall Type I error rate at a 2-sided alpha level of 0.05. A graphical approach will be used to perform the multiplicity-controlled analyses as described in Section 6.6.

Primary outcome IGA 0/1 ad EASI-75 and their analysis are described in [Table KGAB.6.11](#).

6.11.2. Sensitivity Analyses of Primary Outcome

Sensitivity analyses are included to demonstrate robustness of analyses. Tipping point analysis as described in Section 6.4.1.2 will serve as the sensitivity analyses for primary outcomes.

Sensitivity and supplementary analyses for both primary and secondary endpoints are described in [Table KGAB.6.11](#) and [Table KGAB.6.12](#).

There will be no adjustment for multiple comparisons for additional analyses of the primary outcome.

6.11.3. Major Secondary Efficacy Analyses

Major secondary outcomes and their analyses are described in [Table KGAB.6.11](#) and [Table KGAB.6.12](#).

6.11.4. Other Secondary Efficacy Analyses

Other secondary outcomes and their analyses are described in [Table KGAB.6.11](#) and [Table KGAB.6.12](#).

